5.7. RESPONDER ANALYSIS

The proportion of patients with improvement, who were stable, or who deteriorated (as defined in section 4.2 using both the primary and the potential sensitivity thresholds if these are suggested by the psychometric analysis) will be summarized at each PRO assessment visit by treatment arms. The denominator in this descriptive analysis will be the number of patients with non-missing data at the particular visit. The analysis will be performed on the ITT population and include only subjects who have an assessment at baseline and at least one post-baseline assessment.

The proportion of patients with definitive deterioration and transient deterioration during the course of the study will be summarized by treatment arms. The denominator in this descriptive analysis will be the number of patients with at least one deterioration during the study.

The analysis will be performed on the ITT population and for each of the following PRO scale scores:

- CARES: TSS and other potential subscales resulting from the psychometric analysis
- PROMIS Fatigue: total, symptoms and impact domain from the 13-item set, as well as other potential subscales resulting from the psychometric analysis

5.8. TIME TO EVENT ANALYSIS

For all time to event analyses, the time to deterioration will be analysed in months and will be presented by treatment group.

TTFD and TTCD will be defined as explained in Section 4.3. The non-parametric Kaplan-Meier method will be used to estimate the survival curves for TTFD and TTCD for each PRO scale score. The 50th percentile of Kaplan-Meier estimates will be used to estimate the median duration of TTFD and TTCD. A two-sided 95% CI will be provided for these estimates. The treatment difference in survival will be assessed by the stratified log-rank test (baseline haemoglobin (≥ 11 or < 11 g/dL) and CKD stage (3, 4 or 5)). Separate log-rank tests will be performed for each of the experimental arms vs. placebo. A Kaplan-Meier plot by treatment group will be presented.

Kaplan-Meier analysis will be performed using PROC LIFETEST (SAS procedure).

A stratified Cox proportional hazard model with Efron's method of tie handling will be used to assess the magnitude of the treatment difference (ie., the hazard ratio), using baseline hemoglobin (≥ 11 or < 11 g/dL) and CKD stage (3, 4 or 5) as stratification factor. The hazard ratio and its 95% CI from the stratified Cox model for each of the experimental arms vs. placebo will be reported.

The analysis will be performed on the ITT population and for each of the following PRO scale scores:

- CARES: TSSE and other potential subscales resulting from the psychometric

Document: \\ieedc-vnasc01\Sites\[\NLHOF\IntProjects\Consulting\Projects\Corvidia\Biostatistics\01.Documentation\02.SAPI\Corvidia_RESCUE_PROSAP_v2.0_21JUL2020
Author: [REDACTED] Version No: v.2.0
Template No.: [REDACTED] Version Date: 21JUL2020
Effective Date: 01Dec2018 Reference: [REDACTED]

Copyright © 2018 [REDACTED] All rights reserved. The contents of this document are confidential and proprietary to [REDACTED] and its subsidiaries. Unauthorized use, disclosure or reproduction is strictly prohibited.

analysis

- PROMIS Fatigue: total, symptoms and impact domain from the 13-item set, as well as other potential subscales resulting from the psychometric analysis

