4.3.1. TIME TO FIRST CLINICALLY MEANINGFUL DETERIORATION (TTFD)

TTFD will be defined as the duration of time from the date of randomization to the date of the first deterioration in PRO scores of at least one threshold-point (see section 4.2 for the definition of deterioration) as compared to the baseline score.

For those patients who experienced a first clinically meaningful deterioration, TTFD will be computed as follows and then converted to months:

TTFD = Date of assessment when first clinically meaningful deterioration of at least one threshold unit was observed – Date of randomization + 1

Patients who did not experience clinically meaningful deterioration will be censored at the date of the last available PRO assessment (i.e., date of the last non-missing value). Patients with no baseline assessment or patients with no post-baseline assessments will be censored at the date of randomization.

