5. STATISTICAL METHODOLOGY

5.1. GENERAL CONSIDERATIONS

Continuous data will be described by the number of observations (N), the number of missing observations (Nmiss), mean, SD, median, minimum (min), and maximum (max). Categorical data will be described by the number (n) and percentage (%) of patients in each category. Missing and invalid observations will be tabulated as separate categories. The calculation of proportions will not include the missing/invalid category.

Statistical comparisons will be made using two-sided tests at the $\alpha = 0.05$ significance level unless stated otherwise. Due to the exploratory nature of the analyses, adjustments for multiple comparisons will not be made.

Unless otherwise specified, all summaries will be presented by treatment group.

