5.6.1. MMRM

All PRO assessments will be included for this analysis. The analysis will be based on observed data, i.e., data collected at each timepoint without carrying forward previous values. Data from a limited number of PRO assessments may be used in case of substantial dropout (i.e., analysis will be limited to timepoints at which at least 10% of patients have non-missing data in both treatment groups).

The response variable will be the change from baseline to each PRO assessment. The model will include the treatment arm (ziltivekimab vs. placebo) and timepoint (Week 5, Week 13, and week 24) as fixed-effect categorical factors, the baseline PRO score and stratification factors (baseline haemoglobin (≥ 11 or < 11 g/dL) and CKD stage (3, 4 or 5)), as well as the baseline PRO score x time and treatment x time interactions. Both main effects and the interaction terms will remain in the model, regardless of significance. The model will present least squares (LS) mean estimates for each dose, least squares mean differences of each study drug dose from placebo, standard errors, 95% CIs and p-values (where applicable) for mean changes from baseline to each visit. A plot of the LS means accompanied by the 95% CI will be produced.

In addition, an overall adjusted mean estimate will be derived that will estimate the average change from baseline across all time points, giving each visit equal weight.

The standardized mean difference (SMD) including 95% CI (Hedges' g) will also be provided.

The MMRM analysis will be conducted using PROC MIXED in SAS. The model will assume unstructured covariance among the within-patient repeated measurements. If the algorithm does not converge, a heterogeneous Toeplitz (the TOEPH option in SAS PROC MIXED) will be tried first and then AR(1) as a covariance structure to achieve convergence. The Kenward-Roger approximation will be used to estimate denominator degrees of freedom.

Variables listed as categorical in the list above will be included in the CLASS statement of the procedure. The unique patient identifier will also be included as a class variable. A REPEATED statement over the visits will be included with the unique patient identifier as the SUBJECT variable in the REPEATED statement.

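### PRO SAP v2.0 section 5.8 leaves the baseline score of the analysed scale out of the time-to-deterioration Cox model, a small and avoidable loss of precision in a supportive analysis

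*SAP*

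**What the plan says.** Section 5.8 of the PRO SAP v2.0 compares each dose with placebo in two ways. For the test: "The treatment difference in survival will be assessed by the stratified log-rank test (baseline haemoglobin" category and CKD stage). For the estimate, a stratified Cox model "will be used to assess the magnitude of the treatment difference (ie., the hazard ratio), using baseline hemoglobin" category and CKD stage as strata. The output is defined as follows: "The hazard ratio and its 95% CI from the stratified Cox model for each of the experimental arms vs. placebo will be reported". No baseline PRO score appears as covariate or stratum in either. The superseded v1.0 specified treatment as the single covariate; v2.0 drops that phrase and names no other covariate.

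The event in section 4.3.1 is the "first deterioration in PRO scores of at least one threshold-point (see section 4.2 for the definition of deterioration) as compared to the baseline score". Section 4.3.2 builds definitive deterioration on the same change from baseline. Patients without an event "will be censored at the date of the last available PRO assessment"; those with no baseline or no post-baseline assessment are censored at randomisation.

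Section 5.6.1 models change in the same scores with "the baseline PRO score and stratification factors", plus a baseline-by-time interaction.

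Time to deterioration is a supportive objective (section 1.1). Section 5.1 calls the PRO analyses exploratory and makes no multiplicity adjustment.

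**The concern.** A patient who starts with a high (bad) score tends to drift down and one who starts low tends to drift up, so the baseline score predicts who crosses a change threshold. The plan acts on this in the MMRM but not in the Cox model.

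Two things are at stake. Leaving a prognostic covariate out of a Cox model costs power. And the arm that happens to start with worse scores records fewer deteriorations whatever the treatment does, so a chance imbalance moves the hazard ratio in the trial at hand.

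Section 5.8 yields at least 24 hazard ratios: 3 doses × 2 endpoints × 4 scales (CARES TSS; PROMIS Fatigue total, symptom and impact). Some imbalance on some scale is therefore to be expected.

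**Working it through.** **The plan's own figures.** No power, event count or hazard ratio is stated for time to deterioration. The only sample-size figure is for hs-CRP: a difference of 60.74 with SD 16.893 and 54 per group gives power above 99%, and 54/0.9 = 60 per group. Both reproduce, but neither bears on this point.

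**Inputs from the documents.** 60 patients per arm planned (PRO SAP 2.2). About 140 completers and more than 120 non-completers (section 1), so about 260/4 = 65 per arm and 120/260 = 46% without Week 24 data. Assessments at Weeks 5, 13 and 24. Four strata: two haemoglobin categories × two CKD categories (clinical SAP 2.2.2.1 combines stages 4 and 5). Two-sided 5% tests.

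**Assumptions.** A threshold of 0.5 baseline SD (one of the distribution-based methods in PAP 7.3.8.1; the final value is not given), the correlation ρ between visits, the benefit in SD units, normal scores, and Week 24 missingness unrelated to outcome. No floor or ceiling was modelled.

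**Why baseline predicts the event.** With unit-variance scores, the expected change given baseline y₀ (in SD from the mean) is −(1−ρ)y₀, and corr(change, baseline) = −√((1−ρ)/2). This is −0.50 at ρ = 0.5, −0.39 at 0.7 and −0.32 at 0.8, so the covariate matters less as ρ rises. In simulation without a treatment effect, the hazard ratio per 1 SD higher baseline is 0.48, 0.53 and 0.59 at ρ = 0.5, 0.6 and 0.75.

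**Power of the stratified Cox model without and with the baseline score.**

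| Setting | ρ | Benefit | Without | With | Gain (points) |
|---|---|---|---|---|---|
| 65 per arm, 250 runs | 0.5 | 0.4 SD | 49% | 57% | 8 |
| | 0.6 | 0.4 SD | 54% | 60% | 6 |
| | 0.75 | 0.4 SD | 78% | 79% | 1 |
| 65 per arm, 600 runs | 0.5 | 0.4 SD | 49.5% | 57.2% | 7.7 |
| | 0.6 | 0.4 SD | 57.8% | 66.7% | 8.9 |
| 60 per arm, 1000 runs | 0.5 | 0.3 SD | 30.6% | 35.8% | 5.2 |
| | 0.7 | 0.3 SD | 42.4% | 46.5% | 4.1 |
| | 0.8 | 0.3 SD | 55.5% | 56.5% | 1.0 |

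The Monte Carlo standard error is about 3 points per power figure with 250 runs, and about 2 points for the paired gain with 600 runs. The two results at ρ = 0.6 (gains of 6 and 9) show how uncertain the upper end is.

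In the 1000-run simulation the mean log hazard ratio without and with the covariate is −0.42 and −0.47 (ρ = 0.5), −0.57 and −0.61 (0.7), −0.77 and −0.80 (0.8).

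**Validity and chance imbalance, no treatment effect, 60 per arm, 1000 runs.** The SD of the chance difference in baseline means is √(2/60) = 0.18, so 0.2 SD is an ordinary imbalance.

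| ρ | Rejection without / with | Slope of log HR per 1 SD imbalance, without / with | HR without covariate at no imbalance | HR without covariate at 0.2 SD |
|---|---|---|---|---|
| 0.5 | 4.8% / 3.4% | −0.66 / 0.00 | 0.98 | 0.86 |
| 0.7 | 4.9% / 4.2% | −0.57 / −0.02 | 1.00 | 0.89 |
| 0.8 | 5.3% / 5.5% | −0.46 / 0.00 | 0.99 | 0.90 |

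For example, at ρ = 0.5: 0.98 × exp(−0.66 × 0.2) = 0.98 × 0.876 = 0.86. The imbalance here is a worse baseline on active treatment; the reverse imbalance pushes the hazard ratio above 1. The mean log hazard ratio without the covariate lies between −0.019 and 0.007, that is, a hazard ratio of 0.98 to 1.01.

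**The case against.** The strongest reply is that nothing here is wrong. A log-rank test and Cox model stratified by the randomisation factors are conventional and valid, and an MMRM of mean change and a first-event analysis answer different questions, so different covariates are no contradiction. That stands.

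A reader might infer that the planned hazard ratio is biased. That is not supported: patients are randomised, and over repeated randomisation the null hazard ratio averages about 1 with type I error of about 5%. What remains is a shift conditional on the imbalance that happens to occur. Nor does the move away from 1 after adjustment show an error in the planned estimate. Part of it is non-collapsibility: the unadjusted and adjusted hazard ratios are different quantities.

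A reader might also infer a larger effect from the bounded scales, since a patient near the top has little room to worsen. This is plausible, but floor and ceiling effects were not modelled and the documents give no score distributions.

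The size of the gain rests on assumed inputs. CARES scores are averages over 7 or 14 days and PROMIS Fatigue sums 13 items, so the high correlations, where the gain is about 1 point, are at least as plausible as the low ones. The MMRM for the key objective already adjusts for baseline, and the tables of scores by arm in section 5.5.2 would reveal an imbalance. These facts limit the severity. They do not explain why a score already collected, on which the event itself depends, is left out.

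**Conclusion.** The omission is real, and no other section supplies the covariate. It is a weakness of efficiency and precision, not an invalid test. The cost is roughly 1 to 9 points of power across assumed correlations of 0.5 to 0.8 and benefits of 0.3 to 0.4 SD, near zero at the high correlations. An ordinary baseline imbalance of about 0.2 SD moves a null hazard ratio to about 0.86 to 0.90; with the covariate that sensitivity nearly disappears. These figures depend on the assumed 0.5 SD threshold, normal scores and 46% missing at Week 24.

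Severity is low, since the analysis is supportive and exploratory. The finding gives no reason to replace or demote the log-rank test.

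**What to change.** In section 5.8, state that the stratified Cox model for each dose versus placebo includes the baseline score of the analysed scale as a continuous covariate. Report its hazard ratio and 95% CI, labelled as conditional on baseline score so that a difference from the unadjusted results is not read as an inconsistency. Keep the stratified log-rank test and Kaplan-Meier curves as planned.

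The cost is one sentence and one model term, specified before database lock as section 1 requires of any revision. No evaluable patient is lost, because those without a baseline score are already censored at randomisation. The added assumption is a linear effect of baseline on the log hazard; the retained log-rank test does not rely on it.

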5.9. HANDLING OF MISSING DATA

5.9.1. MISSING ITEMS

In case of missing items, the scores will be calculated as indicated in the scoring manuals for each of the PRO instruments.

5.9.2. MISSING FORMS

It is anticipated that the great majority of missing data in this study will have a monotone pattern, meaning that once a patient has missing data at one visit, data will be missing at all subsequent visits. There may be some small amount of intermittent (non-monotone) missing data (when patient skips intermediate visits but return for evaluations at subsequent visits). The number and percentage of patients for each of the missing data patterns (no missing data, monotone missing data, and intermittent missing data) will be presented by treatment group.

Tabular summaries for the percentage of patients by the reason for discontinuation of study treatment, as well as for withdrawal from the study, are provided in the clinical SAP and will not be repeated herein. A plot of the mean PRO score for selective scores (e.g., CARES TSS and other potential subscales resulting from the psychometric analysis, PROMIS Fatigue: total, symptoms and impact scales from the 13-item set, as well as other potential subscales resulting from the psychometric analysis) over time by selected categories of discontinuation (including completers) will be provided. The reasons of discontinuation will be grouped as follows:

- Death
- Adverse event
- Disease relapse, lack of efficacy, and progressive disease
- Other (lost to follow-up, non-compliance with study drug, pregnancy, protocol deviation, recovery, site terminated by sponsor, technical problems, withdrawal by parent/guardian, withdrawal by subject, other)
- COVID19 pandemic.

6. ANALYSIS SOFTWARE

All data processing, summarization, and analyses will be performed using SAS Version 9.4 (SAS Institute, North Carolina) or higher.

Document: \\ieedc-vnasc01\Sites\[\NLHOF\IntProjects\Consulting\Projects\Corvidia\Biostatistics\01.Documentation\02.SAPI\Corvidia_RESCUE_PROSAP_v2.0_21JUL2020
Author: [REDACTED] Version No: v.2.0
Template No.: [REDACTED] Version Date: 21JUL2020
Effective Date: 01Dec2018 Reference: [REDACTED]

Copyright © 2018 [REDACTED] All rights reserved. The contents of this document are confidential and proprietary to [REDACTED] and its subsidiaries. Unauthorized use, disclosure or reproduction is strictly prohibited.

8. APPENDICES

8.1. APPENDIX A. CARES

The image displays four screenshots of a mobile application titled "Symptom Inventory" across four pages (1/20, 2/20, 3/20, 4/20). Each screen shows a progress bar at the top, a "Next" button at the bottom, and a 10-point rating scale for symptoms. The symptoms are:

- Symptom 1:** Progress 1/20. Question: "Please tell us about your chronic kidney disease symptoms during the past 24 hours." Instructions: "Please click the Next button below to continue." Rating scale: 0 (No shortness of breath) to 10 (Shortness of breath as bad as I can imagine).
- Symptom 2:** Progress 2/20. Question: "During the past 24 hours" (repeated). Rating scale: 0 (No shortness of breath) to 10 (Shortness of breath as bad as I can imagine).
- Symptom 3:** Progress 3/20. Question: "During the past 24 hours" (repeated). Rating scale: 0 (No swelling) to 10 (Swelling as bad as I can imagine).
- Symptom 4:** Progress 4/20. Question: "During the past 24 hours" (repeated). Rating scale: 0 (No fatigue) to 10 (Fatigue (weariness, tiredness) as bad as I can imagine).

Symptom Inventory
 
5 / 20 Progress
 
During the past 24 hours
 
Rate your worst weakness.
 
Selected Value:
 

0	1	2	3	4	5	6	7	8	9	10	

No weakness		Weakness as bad as I can imagine	

 
← Previous Next →
	0	1	2	3	4	5	6	7	8	9	10	No weakness						Weakness as bad as I can imagine					
Symptom Inventory
 
6 / 20 Progress
 
During the past 24 hours
 
Rate your worst light-headedness / dizziness.
 
Selected Value:
 

0	1	2	3	4	5	6	7	8	9	10	

No light-headedness / dizziness		Light-headedness/ dizziness as bad as I can imagine	

 
← Previous Next →
	0	1	2	3	4	5	6	7	8	9	10	No light-headedness / dizziness						Light-headedness/ dizziness as bad as I can imagine				
0	1	2	3	4	5	6	7	8	9	10																																			
No weakness						Weakness as bad as I can imagine																																							
0	1	2	3	4	5	6	7	8	9	10																																			
No light-headedness / dizziness						Light-headedness/ dizziness as bad as I can imagine																																							

Symptom Inventory
 
7 / 20 Progress
 
During the past 24 hours
 
Rate your decreased appetite.
 
Selected Value:
 

0	1	2	3	4	5	6	7	8	9	10	

No decreased appetite		Decreased appetite as bad as I can imagine	

 
← Previous Next →
	0	1	2	3	4	5	6	7	8	9	10	No decreased appetite						Decreased appetite as bad as I can imagine					
Symptom Inventory
 
8 / 20 Progress
 
During the past 24 hours
 
Rate your worst nausea.
 
Selected Value:
 

0	1	2	3	4	5	6	7	8	9	10	

No nausea		Nausea as bad as I can imagine	

 
← Previous Next →
	0	1	2	3	4	5	6	7	8	9	10	No nausea						Nausea as bad as I can imagine				
0	1	2	3	4	5	6	7	8	9	10																																			
No decreased appetite						Decreased appetite as bad as I can imagine																																							
0	1	2	3	4	5	6	7	8	9	10																																			
No nausea						Nausea as bad as I can imagine																																							

Document: \\ieedc-vnasc01\Sites\ [REDACTED]\NLHOF\IntProjects\Consulting\Projects\ Corvidia\ [REDACTED]
Biostatistics\01.Documentation\02.SAPI Corvidia_RESCUE_PROSAP_v2.0_21JUL2020
Author: [REDACTED] Version No: v.2.0
Template No.: [REDACTED] Version Date: 21JUL2020
Effective Date: 01Dec2018 Reference: [REDACTED]

Copyright © 2018 [REDACTED] All rights reserved. The contents of this document are confidential and proprietary to [REDACTED] and its subsidiaries. Unauthorized use, disclosure or reproduction is strictly prohibited.

Symptom Inventory

9 / 20 Progress

During the past 24 hours

Rate your worst feeling of depressed mood.

Selected Value:

0	1	2	3	4	5	6	7	8	9	10
---	---	---	---	---	---	---	---	---	---	----

No feeling of depressed mood Feeling of depressed mood as bad as I can imagine

← Previous Next →

Symptom Inventory

10 / 20 Progress

During the past 24 hours

Rate your worst difficulty concentrating.

Selected Value:

0	1	2	3	4	5	6	7	8	9	10
---	---	---	---	---	---	---	---	---	---	----

No difficulty concentrating Difficulty concentrating as bad as I can imagine

← Previous Next →

Symptom Inventory

11 / 20 Progress

During the past 24 hours

Rate your forgetfulness.

Selected Value:

0	1	2	3	4	5	6	7	8	9	10
---	---	---	---	---	---	---	---	---	---	----

No forgetfulness Forgetfulness as bad as I can imagine

← Previous Next →

Symptom Inventory

12 / 20 Progress

During the past 24 hours

Rate the worst pain in your bones / joints.

Selected Value:

0	1	2	3	4	5	6	7	8	9	10
---	---	---	---	---	---	---	---	---	---	----

No pain in bones / joints Pain in bones / joints as bad as I can imagine

← Previous Next →


Symptom Inventory
 
13 / 20 Progress
 
During the past 24 hours
 
Rate your worst nerve pain.
 
Selected Value:
 

0	1	2	3	4	5	6	7	8	9	10	

No nerve pain		Nerve pain as bad as I can imagine	

 
← Previous Next →
	0	1	2	3	4	5	6	7	8	9	10	No nerve pain						Nerve pain as bad as I can imagine					
Symptom Inventory
 
14 / 20 Progress
 
During the past 24 hours
 
Rate your worst muscle cramps.
 
Selected Value:
 

0	1	2	3	4	5	6	7	8	9	10	

No muscle cramps		Muscle cramps as bad as I can imagine	

 
← Previous Next →
	0	1	2	3	4	5	6	7	8	9	10	No muscle cramps						Muscle cramps as bad as I can imagine					
Symptom Inventory
 
15 / 20 Progress
 
During the past 24 hours
 
Rate the worst numbness / tingling in your hands or feet.
 
Selected Value:
 

0	1	2	3	4	5	6	7	8	9	10	

No numbness / tingling in hands or feet		Numbness / tingling in hands or feet as bad as I can imagine	

 
← Previous Next →
	0	1	2	3	4	5	6	7	8	9	10	No numbness / tingling in hands or feet						Numbness / tingling in hands or feet as bad as I can imagine					
Symptom Inventory
 
16 / 20 Progress
 
During the past 24 hours
 
Rate your worst uncomfortable sensation in your legs.
 
Selected Value:
 

0	1	2	3	4	5	6	7	8	9	10	

No uncomfortable sensation in legs		Uncomfortable sensation in legs as bad as I can imagine	

 
← Previous Next →
	0	1	2	3	4	5	6	7	8	9	10	No uncomfortable sensation in legs						Uncomfortable sensation in legs as bad as I can imagine				
0	1	2	3	4	5	6	7	8	9	10																																																																																	
No nerve pain						Nerve pain as bad as I can imagine																																																																																					
0	1	2	3	4	5	6	7	8	9	10																																																																																	
No muscle cramps						Muscle cramps as bad as I can imagine																																																																																					
0	1	2	3	4	5	6	7	8	9	10																																																																																	
No numbness / tingling in hands or feet						Numbness / tingling in hands or feet as bad as I can imagine																																																																																					
0	1	2	3	4	5	6	7	8	9	10																																																																																	
No uncomfortable sensation in legs						Uncomfortable sensation in legs as bad as I can imagine																																																																																					

Document: \\ieedc-vnasc01\Sites\ [REDACTED]\NLHOF\IntProjects\Consulting\Projects\ Corvidia\ [REDACTED]
Biostatistics\01.Documentation\02.SAPI Corvidia_RESCUE_PROSAP_v2.0_21JUL2020
Author: [REDACTED] Version No: v.2.0
Template No.: [REDACTED] Version Date: 21JUL2020
Effective Date: 01Dec2018 Reference: [REDACTED]

Copyright © 2018 [REDACTED] All rights reserved. The contents of this document are confidential and proprietary to [REDACTED] and its subsidiaries. Unauthorized use, disclosure or reproduction is strictly prohibited.


Symptom Inventory
 
17 / 20 Progress
 
During the past 24 hours
 
Rate your worst itching.
 
Selected Value:
 

0	1	2	3	4	5	6	7	8	9	10	

No itching		Itching as bad as I can imagine	

 
← Previous Next →
	0	1	2	3	4	5	6	7	8	9	10	No itching						Itching as bad as I can imagine					
Symptom Inventory
 
18 / 20 Progress
 
During the past 24 hours
 
Rate your worst dry skin.
 
Selected Value:
 

0	1	2	3	4	5	6	7	8	9	10	

No dry skin		Dry skin as bad as I can imagine	

 
← Previous Next →
	0	1	2	3	4	5	6	7	8	9	10	No dry skin						Dry skin as bad as I can imagine					
Symptom Inventory
 
19 / 20 Progress
 
During the past 24 hours
 
Rate your worst feeling of dry mouth.
 
Selected Value:
 

0	1	2	3	4	5	6	7	8	9	10	

No feeling of dry mouth		Feeling of dry mouth as bad as I can imagine	

 
← Previous Next →
	0	1	2	3	4	5	6	7	8	9	10	No feeling of dry mouth						Feeling of dry mouth as bad as I can imagine					
Symptom Inventory
 
20 / 20 Progress
 
During the past 24 hours
 
Rate your worst difficulty with tolerating cold.
 
Selected Value:
 

0	1	2	3	4	5	6	7	8	9	10	

No difficulty with tolerating cold		Difficulty with tolerating cold as bad as I can imagine	

 
← Previous Next ↑
	0	1	2	3	4	5	6	7	8	9	10	No difficulty with tolerating cold						Difficulty with tolerating cold as bad as I can imagine				
0	1	2	3	4	5	6	7	8	9	10																																																																																	
No itching						Itching as bad as I can imagine																																																																																					
0	1	2	3	4	5	6	7	8	9	10																																																																																	
No dry skin						Dry skin as bad as I can imagine																																																																																					
0	1	2	3	4	5	6	7	8	9	10																																																																																	
No feeling of dry mouth						Feeling of dry mouth as bad as I can imagine																																																																																					
0	1	2	3	4	5	6	7	8	9	10																																																																																	
No difficulty with tolerating cold						Difficulty with tolerating cold as bad as I can imagine																																																																																					

8.2. APPENDIX B. PROMIS FATIGUE 13A SHORT FORM, ADDITIONAL FATIGUE ITEMS, SEXUAL ACTIVITY ITEM

PROMIS Items

PROMIS Short Form v1.0 – Fatigue 13a	During the past 7 days.....	Not at all	A little bit	Somewhat	Quite a bit	Very much
	I feel fatigued	1 	2 	3 	4 	5 
	I feel weak all over	1 	2 	3 	4 	5 
	I feel listless ("washed out")	1 	2 	3 	4 	5 
	I feel tired	1 	2 	3 	4 	5 
	I have trouble starting things because I am tired	1 	2 	3 	4 	5 
	I have trouble finishing things because I am tired	1 	2 	3 	4 	5 
	I have energy	1 	2 	3 	4 	5 
	I am able to do my usual activities	1 	2 	3 	4 	5 
	I need to sleep during the day	1 	2 	3 	4 	5 
	I am too tired to eat	1 	2 	3 	4 	5 
	I need help doing my usual activities	1 	2 	3 	4 	5 
	I am frustrated by being too tired to do the things I want to do	1 	2 	3 	4 	5 
	I have to limit my social activity because I am tired	1 	2 	3 	4 	5 
PROMIS items (Item identifier in bold)	FATEXP36: How exhausted were you on average?	1 	2 	3 	4 	5 
	FATEXP43: How physically drained were you on average?	1 	2 	3 	4 	5 
	FATIMP52: To what degree did your fatigue make you feel less alert?	1 	2 	3 	4 	5 
	During the past 30 days.....	Not at all	A little bit	Somewhat	Quite a bit	Very much
	SFINT101: How interested have you been in sexual activity?	1 	2 	3 	4 	5 

Document: \\eedc-vnasc01\Sites\ [REDACTED]\NLHOF\IntProjects\Consulting\Projects\ Corvidia\ [REDACTED]
Biostatistics\01.Documentation\02.SAPI Corvidia_RESCUE_PROSAP_v2.0_21JUL2020
Author: [REDACTED] Version No: v.2.0
Template No.: [REDACTED] Version Date: 21JUL2020
Effective Date: 01Dec2018 Reference: [REDACTED]

Copyright © 2018 [REDACTED] All rights reserved. The contents of this document are confidential and proprietary to [REDACTED] and its subsidiaries. Unauthorized use, disclosure or reproduction is strictly prohibited.

